10.3 Statistical Analysis

10.3.1 General Considerations

Descriptive summary statistics include mean, median, standard deviation, interquartile range, and range (minimum, maximum) for continuous variables, and counts and percentages for categorical

variables. Unless otherwise specified, continuous variables will be analyzed using two-sample t-test or Wilcoxon-Mann-Whitney test, whichever is appropriate; and categorical variables will be analyzed using chi-squared test or Fisher's exact test, whichever is appropriate.

SAS 9.3 or later will be used to perform statistical analysis. Unless otherwise specified, a two-sided p-value less than 0.05 will be considered statistically significant. No multiplicity adjustment will be made.

10.3.2 Background Characteristics

10.3.2.1 Patient Disposition

Both number and percentage of patients in the following categories will be summarized as appropriate:

- Randomized;
- Safety Population;
- ITT Population;
- mITT Population
- PP Population;
- Completed treatment visits; and
- Prematurely discontinued the study and the reasons for discontinuations.

Reasons for discontinuation and major protocol violations will be summarized by treatment groups for the ITT and mITT populations.

10.3.2.2 Demographics, Background, and Baseline Characteristics

Demographics, background (e.g., medical history), and baseline characteristics will be summarized. Protocol deviations/violations will be provided as a patient data listing only. Major protocol deviations/violations will be identified for analysis purposes.

The demographics and baseline characteristics summary will be presented for the ITT, mITT, PP, and safety populations to allow review of the characteristics of those included in the efficacy and safety analyses, which will be based on these analysis populations. Background (e.g., medical history) summary will be presented for the ITT population only.

10.3.2.3 Prior and Concomitant Medications

Medications used in this study will be coded by the World Health Organization Drug Dictionary (WHODD), and summarized as frequency tables for the preferred terms in 2 parts:

- Prior medication: any medication that started prior to the first dose of study drug, regardless of when it ended (collected for medications given up to 6 months prior to Day 1).

- Concomitant medication: medication received at or after dosing of study drug, or medication that was received prior to dosing with study drug and continued after dosing of study drug.

If medication start date is on the day of or after the first dose of study drug, then medication will be summarized as concomitant medication regardless of whether the medication end date is missing or not. If the medication end date is before the date of first dosing of study drug, then the medication will be summarized as prior medication regardless of whether the medication start date is missing or not. Note that medication that started prior to first dosing of study drug and continued after dosing will be summarized as prior medication and separately as concomitant medication. Both prior and concomitant medications will be based on the ITT population. For medications with partial start dates, missing month will be imputed with January and missing day will be imputed with 1. For medications with partial stop dates, missing month will be imputed with December and missing day will be imputed with the last day of the month.

10.3.3 Efficacy Analyses

For all efficacy analyses, the main analysis will be based on the mITT population. Both primary and secondary endpoint analyses will also be performed on the PP population; these analyses will be supportive only. Comparisons will be made between the SelK2 treated patients SelK2 and enoxaparin treated patients, and the enoxaparin group. The difference of the total VTE rate during the Treatment Phase (from time of randomization up until the day of completion of venogram) between the SelK2, SelK2 and enoxaparin, and enoxaparin treatment groups will be estimated. The lower 1-sided 90% CI of the difference will be calculated and non-inferiority will be concluded if the upper limit of the 90% CI is $\leq 15\%$. The same analysis will be completed on the PP population.

The following secondary analyses will be performed on the mITT and PP populations:

- Comparison of the rates of the individual components of the primary efficacy outcome between the SelK2, SelK2 and enoxaparin, and enoxaparin treatment groups through Treatment Period.
- Conduct primary efficacy analysis of the total VTE rate between the SelK2 treatment, SelK2 and enoxaparin treatment, and enoxaparin treatment with the inclusion of events through Study Day 57.
- Complete comparison of the rates of the individual components of the primary efficacy outcome between the SelK2, SelK2 and enoxaparin, and enoxaparin treatment groups with the inclusion of events through Study Day 57.

Absolute changes from baseline in hsCRP and D-dimer will be summarized by treatment group at each post-baseline visit. Change from baseline in each parameter will be analyzed and compared between treatment groups using a mixed linear model with repeated measures (MMRM).

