[REDACTED] Vials are stored refrigerated at 2 to 8°C and protected from light. A pharmacist or designated personnel will compound individual doses of active study drug for patients on a milligram per kilogram basis in a 100 mL infusion bottle or bag of a sterile 0.9% sodium chloride solution (0.9% Sodium Chloride Injection, USP) in accordance with the Pharmacy Manual. Study drug will be administered over 30 minutes by IV infusion.

Active Comparator (Enoxaparin): Commercially available enoxaparin (40 mg in 0.4 mL water

in pre-filled disposable syringes for SC administration) will be provided to the study site pharmacies for use in this study, in accordance with local regulatory requirements. Enoxaparin should be stored in a temperature-controlled environment which is maintained below 25°C; but should not be frozen.

The Pharmacy Manual will provide further details about handling, storage, and mode of administration.

Dose Rationale:

Criteria for Evaluation:

Primary Efficacy Endpoints: The primary efficacy outcome is the composite of asymptomatic deep vein thrombosis (DVT) detected by mandatory unilateral venography of the operated leg or confirmed symptomatic DVT, confirmed symptomatic PE or unexplained death during the Treatment Phase. All efficacy endpoint data will be adjudicated by a blinded Central Independent Adjudication Committee.

Exploratory Efficacy Endpoints: The exploratory efficacy outcomes will include measurements of markers of inflammation and thrombosis (hsCRP and D-dimer, respectively) and other possible PD markers of SelK2 efficacy.

PK, PD, and Immunogenicity Evaluations: Samples will be collected during Treatment and Follow-up Phases for evaluation of PK, PD, and immunogenicity.

Safety:

The primary safety outcome is a composite of major bleeding events or clinically relevant non-major bleeding events during the Treatment Phase. The secondary safety outcomes are the incidence of the composite of major, clinically relevant non-major, or minor bleeding events that occur during the Treatment and Follow-up Phases.

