3.6.2 Exploratory Efficacy Endpoints

3.6.2.1 Laboratory Markers of Inflammation and Thrombosis

Absolute changes from baseline in levels of high sensitivity C-reactive Protein (hsCRP) and D-dimer will be assessed.

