6.5.1.3 Laboratory Markers of Inflammation and Thrombosis

Blood sampling will be collected on Screening, Day 1, Day 4, Day 6 (optional), Day 11, Day 21, and Day 57 for assessment of hsCRP and D-dimer.

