10.0 STATISTICAL METHODS AND PLANNED ANALYSES

10.1 Sample Size and Power

Assuming that the rate of VTE for the active comparator (enoxaparin) arm of this study will be 25%, it is estimated that a sample size of 76 evaluable patients per arm should give the study 80% power of declaring non-inferiority between the SelK2 arm and the enoxaparin active comparator arm. This calculation uses a one-sided 90% CI with a non-inferiority margin of 15%. This calculation assumes that the underlying rate of VTE for the SelK2 and enoxaparin arms will be identical at 25% and with the non-inferiority margin set as at the midpoint between the expected active therapy response compared to an assumed placebo event rate in this patient population of 55%. Consequently, making the conservative estimate that up to 20% of randomized patients may not yield evaluable endpoint data, a total of 95 patients will be enrolled per arm to provide at least 76 endpoint evaluable patients per arm.

Sample Size Considerations for Adaptive Arm:

With the same assumptions as above the for active comparator (enoxaparin) arm of the study event rate, it is estimated that a sample size of 76 evaluable patients in a combination therapy arm of SelK2 and enoxaparin should give the study 80% power of declaring superiority between the SelK2 and enoxaparin arm and the enoxaparin active comparator arm for an estimated SelK2 and enoxaparin VTE event rate of 6% (an 19% difference between combination treatment effect and active comparator treatment effect). This calculation assumes a two-sided 0.1 alpha, a Pearson Chi-squared test, and a superiority comparison.

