10.2 Analysis Populations

Assignment of patients to analysis populations will be done prior to clinical data lock for the study. The following populations will be defined: Intent-to-Treat (ITT), modified Intent-to-Treat (mITT), Per-Protocol (PP), and Safety.

Intent-to-Treat (ITT): All patients who are randomized. The ITT population will be analyzed by randomized treatment group.

Modified Intent-to-Treat (mITT): All patients in the ITT population who also have a successful venogram or symptomatic VTE event which allow for assessment of the primary efficacy outcome.

Per-Protocol (PP): All mITT patients who complete the study and have no major protocol violations that will impact the efficacy assessments.

Safety: All patients who received at least 1 dose of study drug. Safety population will be analyzed by actual treatment received.

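### The mITT rule in Section 10.3.3 also governs the exploratory hsCRP and D-dimer analyses, so it leaves out patients whose markers were measured but whose venogram was not usable (minor)

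*Combined protocol and SAP*

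**What the plan says.** The efficacy rule in Section 10.3.3 is general: "For all efficacy analyses, the main analysis will be based on the mITT population". Section 10.2 limits mITT to ITT patients "who also have a successful venogram or symptomatic VTE event which allow for assessment of the primary efficacy outcome".

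hsCRP and D-dimer fall under that rule. Section 3.6.2.1, under the heading for exploratory efficacy endpoints, says: "Absolute changes from baseline in levels of high sensitivity C-reactive Protein (hsCRP) and D-dimer will be assessed". Section 10.3.3 then plans summaries by visit and an MMRM comparison between treatment groups, and names no other population for them.

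The samples do not depend on the venogram. Section 6.5.1.3 gives the schedule: "Blood sampling will be collected on Screening, Day 1, Day 4, Day 6 (optional), Day 11, Day 21, and Day 57". Table 1 limits the PK/PD and immunogenicity samples to the SelK2-containing arms but puts no such limit on hsCRP and D-dimer.

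ITT is defined in Section 10.2 as "All patients who are randomized. The ITT population will be analyzed by randomized treatment group", but no efficacy or marker analysis is assigned to it. The only other efficacy population used is PP, which is a subset of mITT and so brings nobody back.

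**The concern.** A filter made for one endpoint is applied to another that does not need it. Without a venogram or a symptomatic event, the VTE composite usually cannot be assessed, so restricting that analysis has a reason behind it. The reason does not carry over to a blood marker. A patient with a full hsCRP and D-dimer series and an unreadable or refused venogram has an observed outcome that the main analysis leaves out. This differs from the missing-VTE problem, where the outcome itself is unknown. The MMRM accommodates incomplete series and needs no completeness filter of this kind.

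Two things are at stake. One is precision. The other is that the groups compared are no longer the randomised groups: membership is settled after randomisation, and a patient without a usable venogram stays in only by having had a symptomatic VTE. For D-dimer, which the synopsis names as the marker of thrombosis, that route into the analysis is connected to what is being measured.

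**Working it through.** **Does the rule reach the markers?** Three places have to be read together. Section 10.3.3 covers every efficacy analysis. Sections 3.6.2 and 6.5.1.3 place hsCRP and D-dimer under efficacy. Section 10.2 admits patients to mITT by venogram or symptomatic VTE. Followed as written, the exclusion applies.

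The plan's handling of other blood tests shows the mismatch. Table 1 schedules PT/INR and aPTT at Screening and Days 1, 4, 11, 21 and 57, the same visits as hsCRP and D-dimer apart from the optional Day 6 draw. Under Section 10.4 the coagulation results are analysed in the safety population, with no venogram condition.

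**Inputs (Section 10.1).** VTE rate 25% in both arms, margin 15 percentage points, one-sided 90% confidence interval, 80% power, and an allowance that "up to 20% of randomized patients may not yield evaluable endpoint data".

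**The plan's own figures.**
- n per arm = (z₀.₉₀ + z₀.₈₀)² × 2 × 0.25 × 0.75 / 0.15² = (1.282 + 0.842)² × 0.375 / 0.0225 ≈ 75.1, rounded up to 76. Power at 76 is 80.3%.
- Inflation: 76 / (1 − 0.20) = 95.

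Both reproduce. The difference is 95 − 76 = 19 per arm, or 38 of 190 (20% of 285 = 57 with the adaptive arm).

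**Effect on a marker contrast between two arms of 95.** With equal variances and equal information per patient, the standard error is proportional to 1/√n. Let f be the share of the 19 non-evaluable patients per arm who have usable samples. Then the ratio of the mITT standard error to the all-observed standard error is √((76 + 19f)/76).

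| f (assumed) | Patients with samples left out per arm | Share of randomised | SE ratio |
|---|---|---|---|
| 25% | 4.75 | 5% | 1.031 |
| 50% | 9.5 | 10% | 1.061 |
| 75% | 14.25 | 15% | 1.090 |
| 100% | 19 | 20% | √(95/76) = 1.118 |

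At the ceiling the variance ratio is 95/76 = 1.25.

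**In terms of power, at the ceiling**, using two-sided 0.05 (the default in Section 10.3.1) and a normal approximation:
- An effect with 80% power at 95 per arm has power Φ((1.960 + 0.842) × √(76/95) − 1.960) = Φ(0.546) ≈ 71% at 76.
- The standardised difference detectable with 80% power is 2.802 × √(2/95) = 0.41 SD at 95 per arm and 2.802 × √(2/76) = 0.45 SD at 76.

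**Selection.** Consider two patients without a usable venogram, both with complete marker series. The one with a symptomatic VTE enters mITT; the other does not. Section 6.5.1.2 supports the first route, because a DVT or PE confirmed during the Treatment Phase removes the requirement for venography. The documents give no symptomatic event rate, so the size of any resulting bias cannot be computed.

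**The case against.** The best defence is that little depends on these markers. They are exploratory, even though Section 2.0 lists them under the secondary objectives. Section 10.1 sizes the trial on VTE alone, and the committee data package in Section 10.5 does not list them. That stands, and it sets the severity.

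The rule also concerns the main analysis and does not forbid others. That is true, but no other analysis is specified for these markers beyond the PP subset. Keeping the markers in the same patients as the VTE result is a coherent choice for a mechanistic endpoint; a supportive mITT run preserves it. It is also fair that a set requiring a baseline and a post-baseline value is itself defined after randomisation. It comes closer to the randomised groups without fully restoring them.

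A reader might infer more than the documents support, in three ways:
- **That a fifth of the observed marker data is lost.** The 20% is a conservative planning allowance for missing VTE endpoints. Some of those patients may have withdrawn and lack later samples too, and the documents give no split.
- **That the entry criterion has nothing to do with the markers.** This holds for image quality. It does not hold for the symptomatic-VTE route, which is related to D-dimer.
- **That the marker comparison is biased, or that venogram completion will differ by arm.** Open-label treatment makes a difference possible. However, venography is mandatory on one schedule for all patients and is read blinded, and nothing in the documents predicts an imbalance. Section 1.1 describes venographic DVT after TKA as mainly asymptomatic, so the group entering by symptoms alone may be small.

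**Conclusion.** The point holds as a minor one. Read as written, the plan excludes from its main hsCRP and D-dimer analyses any patient with observed values but no successful venogram and no symptomatic VTE. The cost in precision is at most a 12% larger standard error. That maximum assumes the full 20% non-evaluable rate and usable samples from every excluded patient; the 3% to 9% figures rest on assumed sample availability. Bias for D-dimer is possible, and neither its size nor its direction in the between-arm comparison can be established from the documents. No trial decision rests on these markers.

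**What to change.** Add to Section 10.3.3 that the hsCRP and D-dimer summaries and MMRM use all randomised patients with a baseline value and at least one post-baseline value, analysed by randomised group, and that the same analysis in mITT is supportive. Leave the VTE analyses and their populations unchanged.

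The cost is a short text addition plus the supportive run. The samples and assays are already planned for all patients, so no visits, draws or tests are added.

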Other safety evaluations will include assessment of adverse events, physical examinations, 12-lead ECGs, vital signs (including temperature, respiratory rate, and seated blood pressure and pulse), clinical chemistry laboratory evaluations, additional laboratory evaluations including prothrombin time/international normalized ratio (PT/INR), activated partial thromboplastin time (aPTT), hematology panel, urinalysis, and pregnancy test (female patients of child bearing potential only).

Statistical Methods:

Demographic and other patient data will be summarized by treatment group using descriptive statistics.

The primary efficacy comparison will compare the SelK2 only-treated, SelK2 and enoxaparin-treated, and enoxaparin only-treated arms. The difference in the total VTE rate determined during the entire Treatment Phase will be estimated. The 1-sided lower 90% CI of the difference between the SelK2 and enoxaparin groups only arms as well as the difference between the adaptive arm (SelK2 and enoxaparin) and enoxaparin only arms will be calculated and non-inferiority will be concluded if the upper limit of the 90% CI is $\leq 15\%$. Absolute changes from baseline in levels of high-sensitivity CRP and D-dimer will be assessed. A number of secondary analyses may be conducted to assess the robustness of the primary analysis finding.

SelK2 concentrations will be summarized by descriptive statistics.

Safety will be assessed by reported adverse events, changes from baseline during treatment in vital signs, ECGs, laboratory parameters, and physical examination and will be summarized using descriptive statistics. Adverse events will be coded using the (Medical Dictionary for Regulatory Activities) MedDRA dictionary and summarized by system organ class, preferred term, Investigator causality assessment, and treatment group. Incidence of bleeding events (as adjudicated by CIAC) will be tabulated by treatment group.

Sample Size Considerations:

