8.0 PATIENT WITHDRAWAL, REMOVAL OR SITE TERMINATION

8.1 Withdrawal or Removal of Patient From Study

Patients may withdraw from the study (withdraw consent) or be withdrawn by PI under the following circumstances:

- At their own request or at the request of their legally authorized representative;
- Patient is lost to follow-up;
- Investigator deems it necessary to stop study drug administration (e.g., for safety or for non-compliance to protocol); or
- At the specific request of the Sponsor.

In all cases, the reason for withdrawal must be recorded in the eCRF and in the patient's medical records. The patient must be evaluated to establish whether the reason was an AE, and, if so, this must be reported in accordance with the procedures outlined in Data Handling Procedures (see Section 9.0).

Even if the patient has decided to discontinue from the other study procedures, the Early Discontinuation Visit assessments should be performed approximately eight weeks after the patient's Day 1 (randomization) visit, if possible. In addition, those female patients required to use acceptable birth control during the study must be reminded that they should continue this form of birth control for a total of 10 weeks after receiving a dose of SelK2. The Investigator must make every effort to contact patients lost to follow-up on at least 2 occasions, including sending the patient a letter by certified mail (return receipt).

Occasionally patients may also withdraw consent to allow further data collection. Under such conditions, completion of the scheduled events, procedures, and assessments as specified in the protocol will not be possible. A record of the reason for discontinuation of data collection should be made on the appropriate eCRF page.

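### No VTE analysis covers all randomized patients although up to 20% may be non-evaluable, and Section 8.1 does not say whether the Day 11 venogram goes ahead once study drug is stopped

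*Combined protocol and SAP*

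**What the plan says.** **Analysis sets.** Section 10.2 defines ITT as everyone randomized. It defines mITT as "All patients in the ITT population who also have a successful venogram or symptomatic VTE event", and PP as "All mITT patients who complete the study and have no major protocol violations that will impact the efficacy assessments".

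**Use of the sets.** Section 10.3.3 makes mITT the main set ("For all efficacy analyses, the main analysis will be based on the mITT population"). It adds: "Both primary and secondary endpoint analyses will also be performed on the PP population; these analyses will be supportive only". The listed secondary VTE analyses follow the same pattern: "The following secondary analyses will be performed on the mITT and PP populations". ITT serves for disposition, baseline, medical history and medication summaries (Sections 10.3.2.1 to 10.3.2.3). No efficacy analysis is assigned to it.

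**Expected loss.** Section 10.1 allows that "up to 20% of randomized patients may not yield evaluable endpoint data", and so enrolls 95 per arm to obtain 76.

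**Missing outcomes.** No imputation or sensitivity method is given for a missing VTE outcome. The synopsis (Statistical Methods) says only: "A number of secondary analyses may be conducted to assess the robustness of the primary analysis finding".

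**Withdrawal.** Section 8.1 lists four grounds on which a patient may leave or be removed. One is "Investigator deems it necessary to stop study drug administration (e.g., for safety or for non-compliance to protocol". It does not say whether the venogram still takes place. The Early Discontinuation Visit lists no venography (Section 6.4.5) and is placed about eight weeks after Day 1 (Section 8.1), so it cannot supply the Day 11 outcome.

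**The concern.** Membership of mITT is decided after randomization, and partly by the outcome. A patient with a symptomatic VTE enters without a venogram; a patient with no event and no readable venogram is dropped. Because PP sits inside mITT, the two sets exclude the same non-evaluable patients. If they agree, that says nothing about the patients both have lost.

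Missingness may also be unequal. SelK2 is one infusion before surgery (Section 5.2.1), while enoxaparin runs daily until the venogram (Section 5.2.2). After surgery, the stop-drug ground in Section 8.1 can therefore arise mainly where enoxaparin is continuing, which includes the combination arm. Site staff know the treatment (Section 5.1.2). Blinded adjudication (Section 11.4) protects the reading of a venogram, but not whether one is obtained.

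At stake is whether a non-inferiority claim with a 15-point margin would survive reasonable assumptions about up to a fifth of the patients. A check chosen after open-label data have been seen would carry less weight than one written down now.

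**Working it through.** **Inputs.** From Section 10.1: 25% VTE rate in both arms, margin 15 points, one-sided 90% confidence limit (z = 1.2816), 76 evaluable of 95 enrolled per arm. This leaves 95 − 76 = 19 missing per arm at the full 20%. The plan does not name an interval method; a Wald limit is assumed.

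**1. The plan's own figure.** n = 2 × 0.25 × 0.75 × (1.2816 + 0.8416)² / 0.15² = 75.13, rounded up to 76 per arm; 76 / 0.80 = 95. Both stated figures reproduce.

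**2. mITT result.** Upper limit = d + 1.2816 × √[p(1−p)/76 + 0.25 × 0.75/76], with p = 0.25 + d.
- d = 0: 0 + 1.2816 × 0.0702 = 9.0 points
- d = +3: 3 + 1.2816 × 7.16 = 12.2 points
- d = +5: 5 + 1.2816 × 7.23 = 14.3 points

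All three pass.

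**3. All-randomized tipping rate, imputed outcomes treated as observed.** Hold enoxaparin at 25% in observed and missing patients. Find the SelK2 rate P among 95 at which P − 0.25 + 1.2816 × √[P(1−P)/95 + 0.25 × 0.75/95] = 0.15. The solution is P = 0.3164 (difference 6.64 points, SE 6.52 points). The rate needed in the 19 missing SelK2 patients is r = [95P − 76(0.25 + d)] / 19, with 95P = 30.06:
- d = 0: (30.06 − 19.00)/19 = 58%
- d = +3: (30.06 − 21.28)/19 = 46%
- d = +5: (30.06 − 22.80)/19 = 38%

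**4. With imputation variance.** Step 3 counts imputed patients as if seen. Adding 19r(1−r)/95² to each arm's variance (r = 0.25 for enoxaparin) raises the SE to about 7.1 to 7.2 points and lowers the tipping rates.

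| mITT difference | mITT upper limit | Tipping rate, step 3 | Tipping rate with imputation variance |
|---|---|---|---|
| 0 | 9.0 | 58% | 54% |
| +3 | 12.2 | 46% | 42% |
| +5 | 14.3 | 38% | 34% |

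**5. Same check in whole events.** With 19/76 events observed in each arm, the all-randomized result fails once missing SelK2 patients have 7 more events than missing enoxaparin patients. For 7 against 0, the comparison is 26/95 with 19/95: difference 7.4 points, upper limit 15.2. The pairs 9 against 2 and 12 against 5 also fail.

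**6. Unequal missingness.** Assume true rates at the margin (SelK2 40%, enoxaparin 25%), 76 SelK2 patients evaluable and representative, and a fraction f of 95 enoxaparin patients missing with true rate r. The observed enoxaparin rate is (0.25 − f·r)/(1 − f). For f = 20% and r = 10% it is (0.25 − 0.02)/0.80 = 28.75%.

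| Enoxaparin missing | Error if r = 10% | Error if r = 25% | Error if r = 40% |
|---|---|---|---|
| 5% | 12.0% | 10% | 8.2% |
| 10% | 14.6% | 10% | 6.5% |
| 20% | 21.4% | 10% | 3.6% |

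The nominal one-sided error is 10%. It can move either way, depending on who is missing.

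**The case against.** The defence has real substance, and it limits what can be claimed.

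- **Withdrawal is permissive and not tied to an arm.** A reader might infer that Section 8.1 creates missing outcomes in the enoxaparin arms only. The documents do not support that. None of the four grounds names an arm, Section 7.4 provides for stopping a SelK2 infusion, and the wording is that patients may be withdrawn. Sections 6.5.1.2 and 6.5.2.1.1 describe stopping or withholding enoxaparin without mentioning withdrawal. What stands is the silence about the venogram and a possible imbalance after surgery.
- **Non-evaluable is not the same as no venogram.** The 20% is an upper, conservative allowance. It includes venograms that were done but could not be read (Section 6.5.1.1), which a change to Section 8.1 cannot recover.
- **Not every efficacy analysis is limited to complete cases.** hsCRP and D-dimer are analyzed by MMRM, and the synopsis leaves robustness analyses open. That sentence is optional, however, and names neither method nor population.
- **Unequal evaluability would not go unseen.** Section 10.3.2.1 gives mITT counts and discontinuation reasons by treatment group, and Section 10.3.2.2 gives baseline data for both ITT and mITT. These would reveal an imbalance but not its effect on the conclusion.
- **20% and 15 points are different kinds of quantity.** One is a share of patients and the other a risk difference. With 20% missing in each arm, a 15-point shift in the all-randomized difference needs missing-patient rates 15/0.20 = 75 points apart. The tipping rate is the relevant measure.
- **The +5 case starts only 0.7 points inside the margin**, so modest changes will tip it. This is fair, and is why the three cases are shown together.

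**Conclusion.** The point holds, with limits. Every primary and secondary VTE analysis in Section 10.3.3 is restricted to patients with an assessable outcome, none uses ITT, and comparing mITT with PP cannot test the missing-outcome assumption. Section 8.1 leaves it open whether the Day 11 venogram follows once drug is stopped.

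At a zero observed difference, missing SelK2 patients would need a VTE rate of about 54% to 58% to reverse the conclusion. That is close to the 55% that Section 10.1 assumes for placebo, so the planning case is fairly robust. At +3 and +5 points, rates of about 42% to 46% and 34% to 38% would suffice, so a pass near the margin is fragile.

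These figures rest on 20% missing in each arm, enoxaparin at 25% in observed and missing patients alike, and Wald limits. They do not predict bias, and nothing in the documents shows which treatment it would favor. This is a worthwhile, inexpensive improvement; it does not show that mITT is the wrong main analysis.

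**What to change.** **Section 10.3.3.** Keep mITT as the main analysis. Add a pre-specified sensitivity analysis of the primary endpoint on all randomized patients:
- multiple imputation of missing VTE outcomes by arm, using baseline covariates and whatever D-dimer values are available. Site should stay out of the model: about 25 sites with 95 patients per arm is roughly four per arm per site.
- a two-way tipping-point table of assumed VTE rates in the missing patients of each arm, reported beside the primary result. A fixed cut-off such as 25% to 55% is not needed: those are planning rates, with no established standing as a threshold for missing patients.

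**Section 8.1.** State that stopping study drug is not in itself leaving the study. The already planned Day 11 venogram and follow-up then stay scheduled unless the patient withdraws consent or Section 6.5.1.2 waives the venogram. This concerns outcome collection only and leaves treatment decisions untouched.

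**Cost.** A little more analysis work and a few lines of text, with no change to sample size or visit schedule. The downside is that a positive result may look less robust.
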